3.3 SELECTION OF POPULATION

Minimum 3,000 patients will be enrolled at approximately 40 sites by as many as 80 or more investigators. The treating physicians will mainly be cardiologists or neurologists. To minimize the selection bias, consecutive patients from each site who meet inclusion criteria will be enrolled in this study.

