5. VARIABLES AND THEIR ASSESSMENT

5.1 EFFECTIVENESS

5.1.1 Endpoint(s) of effectiveness

The effectiveness endpoint is the incidence rate of stroke or systemic embolism (definitions are provided in Section 5.1.2.)

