5.1.2 Assessment of effectiveness

Since the patient follow-up period is only 12 weeks (in case of long-term FU, 24 weeks), it is not possible to perform any meaningful effectiveness assessment of Pradaxa in this NIS. However, since it is a requirement to evaluate also effectiveness in all regulatory requisite NIS in Korea and as requested by **MFDS**, a descriptive analysis of effectiveness endpoint will be performed.

Effectiveness analysis will be performed to the patients who have been on Pradaxa more than 12 weeks (in case of long-term FU, 24 weeks).

The following definitions apply and should be used as a guide when reporting a thrombotic event:

Stroke:

Stroke is an acute onset of a focal neurological deficit of presumed vascular origin lasting for 24 hours or more or resulting in death. The stroke is categorized as ischemic or hemorrhagic or uncertain classification (based on CT or MR scanning or autopsy). Fatal stroke is defined as death from any cause within 30 days of stroke. Severity of stroke will be assessed by modified Rankin Scale (see Table 10.1:4) at discharge from hospital and/or at 3-6 months later (if available).

Systemic embolism:

Systemic embolism is an acute vascular occlusion of the extremities or any organ (kidneys, mesenteric arteries, spleen, retina or grafts), typically documented by angiography, surgery, scintigraphy, or autopsy.

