5.2.2 Assessment of adverse events

5.2.2.1 Definitions of adverse events

Adverse event

An adverse event (AE) is defined as any untoward medical occurrence, including an exacerbation of a pre-existing condition, in a patient in a clinical investigation who received a pharmaceutical product. The event does not necessarily have to have a causal relationship with this treatment.

The following definitions apply and should be used as a guide when reporting a thrombotic event:

Transient ischemic attack (TIA)

TIA is defined as a transient episode of neurological dysfunction caused by focal brain, spinal cord, or retinal ischemia without acute infarction (P11-00444).

Pulmonary embolism

- A patient has to fulfil the following criteria:
 1. Typical symptoms or signs (e.g., dyspnea, left or right sided chest pain worsening on respiration, etc) suggestive of pulmonary embolism
 2. CT pulmonary angiography demonstrating an intraluminal filling defect in segmental or more proximally located pulmonary arteries
 3. High probability ventilation-perfusion lung scan, i.e. at least segmental perfusion defect at perfusion scan with normal ventilation at ventilation scan
- The definition of pulmonary embolism is also met if a patient fulfils at least criteria 2 or 3) above.

Proprietary confidential information. © 2014 Boehringer Ingelheim International GmbH or one or more of its affiliated companies.

Myocardial infarction:

- In patients not undergoing PCI or CABG: A patient has to fulfil either the criteria:
 - Development of significant Q-waves in at least 2 adjacent ECG leads.Or at least 2 of the following three criteria:
 - Typical prolonged severe chest pain of at least 30 min
 - ECG changes suggestive of myocardial infarction including ST-changes of T-wave inversion in the ECG.
 - Elevation of troponin or CK-MB to more than upper level of normal (ULN) or, if CK-MB was elevated at baseline, re-elevation to more than 50% increase above the previous level.
- After PCI (within 24h)
Elevation of troponin or CK-MB* to more than 3xULN or, if CK-MB is elevated at baseline, re-elevation to more than 3xULN and a more than 50% increase above the previous level, and/or developing of significant Q-waves** in at least two adjacent ECG leads.
- After coronary artery bypass grafting (within 72h)

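### Could a transient retinal occlusion enter the effectiveness count at one site as systemic embolism and stay out at another as TIA?

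*Combined protocol and SAP*

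**What the plan says.** Section 5.1.1 sets the endpoint: "The effectiveness endpoint is the incidence rate of stroke or systemic embolism". The same sentence then refers to section 5.1.2 for the definitions.

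Section 5.1.2 defines the two components.

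- Stroke: "Stroke is an acute onset of a focal neurological deficit of presumed vascular origin lasting for 24 hours or more or resulting in death". Imaging or autopsy serves to classify the type; infarction is not a criterion.
- Systemic embolism: "Systemic embolism is an acute vascular occlusion of the extremities or any organ (kidneys, mesenteric arteries, spleen, retina or grafts". The definition adds "typically documented by angiography, surgery, scintigraphy, or autopsy", and sets no minimum duration.

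Section 5.2.2.1, among the adverse event definitions, gives: "TIA is defined as a transient episode of neurological dysfunction caused by focal brain, spinal cord, or retinal ischemia without acute infarction". No time limit is stated.

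Both sets of definitions are introduced by the same sentence: "The following definitions apply and should be used as a guide when reporting a thrombotic event". The flow chart and sections 6.2.2.2 and 6.2.2.3 list effectiveness endpoints and adverse events as separate items at each follow-up visit. No adjudication of endpoints is described.

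**The concern.** The definitions are not mutually exclusive. Retinal events appear under both systemic embolism and TIA. Stroke turns on a 24-hour limit, while TIA turns on the absence of infarction. The two criteria can therefore overlap (24 hours or more without infarction) or leave a gap (non-fatal, under 24 hours, with infarction). No sentence gives an order of precedence, and the definitions are offered only as guidance.

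The study is spread widely: "Minimum 3,000 patients will be enrolled at approximately 40 sites by as many as 80 or more investigators". If the labels competed, identical events could be in the count at one site and out at another. The incidence of stroke or systemic embolism would then depend partly on each physician's habit of naming.

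**Working it through.** The plan states no figure on this point, so the main check sets the definitions against specific events.

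**Step 1: which text governs the endpoint.** Section 5.1.1 points to 5.1.2. The TIA definition belongs to adverse event reporting. Nothing in 5.2.2.1 says that an event fitting TIA is removed from the endpoint, and the two kinds of information are separate items at each visit. One event may be entered under both.

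**Step 2: apply 5.1.2 to the doubtful events.**

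| Event | Meets 5.1.2? | Fits the TIA wording? | In the count? |
|---|---|---|---|
| Transient acute retinal artery occlusion, no infarction | Yes, systemic embolism | Yes | Yes |
| Retinal ischemia under 24 hours, no occlusion, no infarction | No | Yes | No |
| Focal deficit of presumed vascular origin, 24 hours or more, no infarction | Yes, stroke | Arguable, depending on how transient is read | Yes |
| Non-fatal focal deficit under 24 hours, with infarction | No | No | No; collected as an adverse event |

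Each row has one answer. The third is settled because stroke requires "lasting for 24 hours or more or resulting in death" and does not require infarction. The fourth lacks only a protocol-defined name. The adverse event definition is broad enough to capture it, and section 7.3.3 provides for MedDRA coding. Only the first row carries a practical risk: that a site stops at the TIA label.

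**Step 3: size of one misplaced event.** The documents give no expected number of events, so 5, 10 and 20 clear endpoint events are assumed, with all 3,000 patients (1,500 + 1,500, section 7.6) as denominator. One event moves the crude incidence by 100 / 3,000 = 0.033 percentage points. The intervals are exact (Clopper-Pearson) 95% intervals for the assumed count.

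| Clear events assumed | Incidence | 95% interval | With one more event | Relative change |
|---|---|---|---|---|
| 5 | 0.167% | 0.054% to 0.389% | 0.200% | 1/5 = 20% |
| 10 | 0.333% | 0.160% to 0.612% | 0.367% | 1/10 = 10% |
| 20 | 0.667% | 0.408% to 1.028% | 0.700% | 1/20 = 5% |

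The interval widths are 0.389 − 0.054 = 0.335, 0.612 − 0.160 = 0.452 and 1.028 − 0.408 = 0.620 percentage points. One event is therefore 0.033/0.335 = 10%, 0.033/0.452 = 7% or 0.033/0.620 = 5% of the interval width.

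Section 5.1.2 restricts the effectiveness analysis to patients treated for more than 12 weeks (24 weeks for long-term follow-up). The true denominator n will be below 3,000, and the step of 100/n percentage points correspondingly larger. The relative change depends only on the number of events.

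**The case for a change.** The best case for a change is that a physician who records a transient retinal occlusion only as TIA has followed the protocol's wording. The TIA definition is not limited to events that fail 5.1.2. Objective documentation of systemic embolism is described as typical and is not required, so its absence does not decide the label. No adjudication step would catch the difference. The incidence is still reported to the regulator, so its count should be reproducible, and a clarifying sentence would cost almost nothing. A single event could be 5% to 20% of the total under the assumed counts.

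Part of this stands. No sentence says expressly that an event reported as TIA must also be entered as an endpoint when it meets 5.1.2, and adverse event counts by term could shift with the label even though the event itself is captured.

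It does not stand as a missing rule, because 5.1.1 already names the governing section. The proposed precedence statement would largely repeat it. The overlap is also narrower than all transient retinal ischemia, since systemic embolism needs an acute vascular occlusion. The Trial Statistical Analysis Plan, the eCRF and the site materials on adverse event reporting are not in the supplied text; any of them may give further instruction.

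**Conclusion.** No change follows. The overlap in wording is real for one narrow event, transient retinal artery occlusion without infarction. Followed as written, the protocol counts that event, and it gives a definite answer for the other doubtful cases. What remains is a possible recording slip that sites and analysts can resolve from 5.1.1 and 5.1.2. A cross-reference from the TIA definition would be an editorial courtesy.

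The expected effect cannot be derived because the documents give no frequency for such events. One event is worth 0.033 percentage points if all 3,000 patients are analysed, and more in a smaller set.

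Little rests on the result. Effectiveness is the secondary objective (2.2.2), although 7.3.1 lists its analysis as primary. Analyses are descriptive (7.1), no hypothesis is tested (7.2), and 5.1.2 itself says the follow-up is too short for a meaningful effectiveness assessment. The conclusion assumes that endpoint and adverse event entries are not mutually exclusive in the eCRF, as the separate visit items indicate.

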5.2 SAFETY

5.2.1 Endpoint(s) of safety

All reported adverse events in patients who take at least one dose of Pradaxa will be noted.

Endpoints pertaining to safety will be presented descriptively and will include:

- adverse events

Proprietary confidential information. © 2014 Boehringer Ingelheim International GmbH or one or more of its affiliated companies.

- unexpected adverse events
- serious adverse events
- drug-related adverse events
- adverse events leading to discontinuation
- adverse events by intensity, outcome of the event, causality

5.2.2 Assessment of adverse events

5.2.2.1 Definitions of adverse events

Adverse event

An adverse event (AE) is defined as any untoward medical occurrence, including an exacerbation of a pre-existing condition, in a patient in a clinical investigation who received a pharmaceutical product. The event does not necessarily have to have a causal relationship with this treatment.

The following definitions apply and should be used as a guide when reporting a thrombotic event:

Transient ischemic attack (TIA)

TIA is defined as a transient episode of neurological dysfunction caused by focal brain, spinal cord, or retinal ischemia without acute infarction (P11-00444).

Pulmonary embolism

- A patient has to fulfil the following criteria:
 1. Typical symptoms or signs (e.g., dyspnea, left or right sided chest pain worsening on respiration, etc) suggestive of pulmonary embolism
 2. CT pulmonary angiography demonstrating an intraluminal filling defect in segmental or more proximally located pulmonary arteries
 3. High probability ventilation-perfusion lung scan, i.e. at least segmental perfusion defect at perfusion scan with normal ventilation at ventilation scan
- The definition of pulmonary embolism is also met if a patient fulfils at least criteria 2 or 3) above.

Proprietary confidential information. © 2014 Boehringer Ingelheim International GmbH or one or more of its affiliated companies.

Myocardial infarction:

- In patients not undergoing PCI or CABG: A patient has to fulfil either the criteria:
 - Development of significant Q-waves in at least 2 adjacent ECG leads.Or at least 2 of the following three criteria:
 - Typical prolonged severe chest pain of at least 30 min
 - ECG changes suggestive of myocardial infarction including ST-changes of T-wave inversion in the ECG.
 - Elevation of troponin or CK-MB to more than upper level of normal (ULN) or, if CK-MB was elevated at baseline, re-elevation to more than 50% increase above the previous level.
- After PCI (within 24h)
Elevation of troponin or CK-MB* to more than 3xULN or, if CK-MB is elevated at baseline, re-elevation to more than 3xULN and a more than 50% increase above the previous level, and/or developing of significant Q-waves** in at least two adjacent ECG leads.
- After coronary artery bypass grafting (within 72h)
Elevation of CK-MB* to more than 5xULN or, if CK-MB was elevated at baseline, re-elevation to more than 5xULN and a more than 50% increase above the previous level, and/or development of significant Q-waves** in at least two adjacent ECG leads.

*Total CK if CK-MB was not available **A new Q-wave with a duration of at least 0.04 seconds and a depth of more than a quarter of the amplitude of the corresponding R-wave, in at least 2 adjacent leads.

Major bleeding, defined as meeting one or more of the following criteria (R11-1250, P11-05406):

- Overt bleeding associated with a reduction in haemoglobin of at least 20 grams per liter or leading to a transfusion of at least 2 units of blood or packed cells
- Symptomatic bleeding in a critical area or organ: Intraocular, intracranial, intraspinal or intramuscular with compartment syndrome, retroperitoneal bleeding, intra-articular bleeding or pericardial bleeding
- Life-threatening bleeding
- Fatal bleeding

Proprietary confidential information. © 2014 Boehringer Ingelheim International GmbH or one or more of its affiliated companies.

Life-threatening bleeding, as defined as meeting one or more of the following criteria:

- Symptomatic intracranial bleed
- Reduction in haemoglobin of at least 50 grams per liter
- Transfusion of at least 4 units of blood or packed cells, associated with hypotension requiring the use of intravenous inotropic agents
- Necessitated surgical intervention

Deaths

will be classified as being: vascular (including bleeding); non-vascular, due to other specified causes (e.g., malignancy), or unknown cause, when cause is not known.

Serious adverse event

A serious adverse event (SAE) is defined as any AE which results in death, is immediately life-threatening, results in persistent or significant disability / incapacity, requires or prolongs patient hospitalisation, is a congenital anomaly / birth defect, or is to be deemed serious for any other reason if it is an important medical event when based upon appropriate medical judgement which may jeopardise the patient and may require medical or surgical intervention to prevent one of the other outcomes listed in the above definitions.

Always serious adverse events

BI has set up a list of AEs which are defined to be always serious. In order to support the investigator with the identification of these “always serious adverse events”, if a non serious AE is identified to be serious per BI definition, a query will be raised. The investigator must verify the description and seriousness of the event. If the event description is correct, the item “serious” needs to be ticked and an SAE has to be reported in expedited fashion. The list of these adverse events can be found via the eCRF system.

Adverse drug reaction

Adverse drug reaction (ADR) refers to any harmful, unintended reaction to the pharmaceutical product of any dose at which a causal relationship with the pharmaceutical product cannot be ruled out.

Non serious adverse drug reaction

Non serious adverse drug reaction is defined as any ADR which does not meet the SAE criteria.

Proprietary confidential information. © 2014 Boehringer Ingelheim International GmbH or one or more of its affiliated companies.

Intensity of adverse event

The intensity of the AE should be defined based on the following three categories and according to medical and scientific judgment:

Mild: Transient symptoms which are subjective or objective but no interference with the patient's daily activities. No change in dosage is needed to continue the treatment.

Moderate: Marked symptoms with moderate interference with the patient's daily activities. Reduced dosage or unplanned treatment is necessary for the relief of adverse events.

Severe: Considerable and unacceptable interference with the patient's daily activities. Discontinuation of the study drug is required because of significant adverse events.

To ensure that no confusion or misunderstanding of the difference between the terms 'serious' and 'severe' which are not synonymous, it should be noted that SAE does not necessarily correspond to serious or not serious AE to severe ones. All SAEs will be reported regardless of the intensity as mentioned above.

Causal relationship of adverse event

Medical judgment will be used to determine the causal relationship, after considering all relevant factors, including pattern of reaction, temporal relationship, de-challenge or re-challenge, confounding factors such as concomitant medication, concomitant diseases and relevant history. Assessment of causal relationship will be recorded in the eCRF.

Related

- a. Certain: An event occurring in a plausible time relationship to drug administration and that cannot be explained by concurrent disease or other drugs or chemicals. The response to withdrawal of the drug (dechallenge) should be clinically plausible. The event must be definitive pharmacologically or phenomenologically, using a satisfactory rechallenge procedure if necessary.
- b. Probable/Likely: An event with a reasonable time sequence to administration of the drug, unlikely to be attributed to concurrent disease or other drugs or chemicals, and which follows a clinically reasonable response on withdrawal (dechallenge). Rechallenge information is not required to fulfill this definition.
- c. Possible: An event with a reasonable time sequence to administration of the drug, but which could also be explained by concurrent disease or other drugs or chemicals. Information on drug withdrawal may be lacking or unclear.

Unrelated

- d. Unlikely: An event with a temporal relationship to drug administration which makes a causal relationship improbable, and in which other drugs, chemicals or underlying disease provide plausible explanations.

Worsening of the underlying disease or other pre-existing conditions

Proprietary confidential information. © 2014 Boehringer Ingelheim International GmbH or one or more of its affiliated companies.

Worsening of the underlying disease or of other pre-existing conditions will be recorded as an (S)AE in the (e)CRF.

Changes in vital signs, ECG, physical examination, and laboratory test results

Changes in vital signs, ECG, physical examination and laboratory test results will be recorded as an (S)AE in the (e)CRF, if they are judged clinically relevant by the NIS physician.

5.2.2.2 Adverse event and serious adverse event reporting

All adverse events occurring from the start of Pradaxa treatment up to 7 days after last follow-up visit need to be collected, documented and reported to the sponsor using the AE reporting form of eCRF (Attachment 1). All SAEs must be reported with details of non-serious AEs occurring at the same time, within 24 hours of occurrence via telephone/fax to the Clinical Safety Officer (CSO) of BI Korea using the SAE report form (Attachment2). If any new or further information to these events is available, a follow-up SAE report has to be sent to BI. All SAEs and non-serious AEs must include a causal relationship assessment from the physician.

All other Adverse Events must be reported on the eCRFs within 2 weeks to the Sponsor.

Contact details:

Clinical Safety Officer

[contact]

[contact]

Address: Boehringer Ingelheim Korea, Medical Dept.

[name]

Pregnancy

Rarely, patients taking part in non interventional studies can get pregnant. Once a patient enrolled into the study and exposed to Pradaxa becomes pregnant, the NIS physician will stop the drug and report immediately to the sponsor. Drug exposure during pregnancy has to be reported immediately (within 24 hours or next business day, whichever is shorter) to CSO. Furthermore, the details of all the drugs to which the patient exposed at the time of pregnancy will be recorded. The outcome of the pregnancy associated with the drug exposure will be assessed. In the absence of an (S)AE, only the Pregnancy Monitoring Form (Attachment 3) for NIS, not the SAE form is to be completed. The ISF will contain the Pregnancy Monitoring Form (Part A and Part B) and those forms could be downloaded from eCRF website.

Proprietary confidential information. © 2014 Boehringer Ingelheim International GmbH or one or more of its affiliated companies.

5.2.3 Assessment of safety laboratory parameters

This section is not applicable.

5.2.4 Electrocardiogram

This section is not applicable.

5.2.5 Assessment of other safety parameters

This section is not applicable.

5.3 OTHER

This section is not applicable.

5.4 APPROPRIATENESS OF MEASUREMENTS

This section is not applicable.

Proprietary confidential information. © 2014 Boehringer Ingelheim International GmbH or one or more of its affiliated companies.

6. INVESTIGATIONAL PLAN

6.1 VISIT SCHEDULE

The flow chart at the front of the protocol summarizes the data to be collected at each visit. The procedures are further described below.

6.2 DETAILS OF STUDY PROCEDURES AT SELECTED VISITS

6.2.1 Screening and run-in period(s)

This section is not applicable as this is a non-interventional study.

6.2.2 Treatment period(s)

As per regulations, enrolled patients will be followed up for a 12 week or 24 week treatment period. There will be a visit window of ± 2 weeks. To minimize the selection bias at the site level, the goal is to have participating centers reflect a balance between general hospitals and clinics for short-term or long-term surveillances.

